3.1.5 Change from baseline in absolute lymphocyte counts

This is defined as the change from baseline in absolute lymphocyte counts at Days 3, 5, 7, 10, 14 and 28. For this endpoint, baseline is defined as the observation on the date of randomization (Day 1). If no result was obtained on the date of randomization, the last result prior to the date of randomization will be used. Details on visit windows are provided in Section 4.1.

The percent change from baseline at these timepoints will also be derived.

3.1.6 All-cause mortality at Day 90

This is defined as the proportion of subjects who have died due to any cause by Day 90.

If a subject is not known to have already died, they (or a caregiver/relative) will be contacted at Day 90 (± 7 days) to confirm survival status. If a subject is lost to follow-up or has withdrawn consent to be followed-up at this timepoint, the survival status of the subject may be obtained by site personnel by checking publicly available resources (as applicable under local laws).

Subjects alive at Day 90 will be censored at Day 90 and subjects lost to follow-up (i.e. with unknown survival status at Day 90) will be censored at the last time known to be alive.

3.1.7 Alive and discharged from the ICU at Days 14 and 28

This is defined as the proportion of subjects alive and discharged from the ICU at Day 14 and the proportion of subjects alive and discharged from the ICU at Day 28.

For a subject to be considered discharged from the ICU, they must not be in ICU on Day 14 (or Day 28), regardless of whether or not ICU-standard care is reported as not clinically indicated in the CHCSS eCRF.

Only the subject's survival status and ICU status on Day 14 (or Day 28) will be considered for this endpoint. No visit window will be used for this endpoint. If they are admitted to ICU after randomization but are discharged by Day 14 (or Day 28), they will be considered alive and discharged from the ICU at Day 14 (or Day 28).

For the FAS analysis, subjects who withdraw or are lost to follow up on or prior to Day 14 (or Day 28), thus survival status and respiratory status at Day 14 (or Day 28) cannot be assessed, will be included in the denominator of this analysis as though they had died or had a respiratory failure.

For the PPAS analysis, subjects who withdraw or are lost to follow up on or prior to Day 14 (or Day 28), thus survival status and respiratory status at Day 14 (or Day 28) cannot be assessed, will be excluded from this analysis, hence the percentage for each treatment group will be calculated as:

$$\frac{\text{Number of subjects alive and free of respiratory failure at Day 14 (or Day 28)}}{\text{Number of subjects who have died or are still in the study at Day 14 (or Day 28)}} \times 100\%$$

To avoid biased estimates of the proportions at DMC review should they be generated, the subjects included in this analysis (based on the FAS and PPAS definitions) will be restricted to subjects who reached Day 14 (or Day 28) (or would have reached Day 14 (or Day 28) had they not died, withdrawn or been lost to follow up) at the time the analysis. This will be considered the full analysis set evaluable at Day 14 (or Day 28).

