3. PRIMARY AND SECONDARY VARIABLES

3.1 Efficacy variables

3.1.1 Alive and free of respiratory failure at Day 28

The primary endpoint is the proportion of subjects who are alive and free of respiratory failure at Day 28. For the purpose of this study respiratory failure is defined based on resource utilization of any of the following modalities:

- Endotracheal intubation and mechanical ventilation;
- Oxygen delivered by high-flow nasal cannula (heated, humidified, oxygen delivered via reinforced nasal cannula at flow rates >20L/min with fraction of delivered oxygen ≥50%);
- Non-invasive positive pressure ventilation or continuous positive airway pressure;
- Extracorporeal membrane oxygenation.

Only the subject's survival status and respiratory-failure status on Day 28 will be considered for this endpoint. No visit window will be used for this endpoint. If they experience respiratory failure after randomization but recover by Day 28, per the definition above, they will be considered alive and free of respiratory failure at Day 28.

For the FAS analysis, subjects who withdraw or are lost to follow up on or prior to Day 28, thus survival status and respiratory status at Day 28 cannot be assessed, will be included in the denominator of this analysis as though they had died or had a respiratory failure.

For the PPAS analysis, subjects who withdraw or are lost to follow up on or prior to Day 28, thus survival status and respiratory status at Day 28 cannot be assessed, will be excluded from this analysis, hence the percentage for each treatment group will be calculated as:

$$\frac{\text{Number of subjects alive and free of respiratory failure at Day 28}}{\text{Number of subjects who have died or are still in the study at Day 28}} \times 100\%$$

To avoid a biased estimate of the proportion for DMC review, the subjects included in this analysis (based on the FAS and PPAS definitions) will be restricted to subjects who reached Day 28 (or would have reached Day 28 had they not died, withdrawn or been lost to follow up) at the time the analysis. This will be considered the full analysis set evaluable at Day 28.

3.1.2 Alive and free of respiratory failure at Day 14

This is defined as the proportion of subjects who are alive and free of respiratory failure at Day 14. Respiratory failure is defined the same as specified in Section 3.1.1 above.

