4.3.2.4 Change from baseline in absolute lymphocyte count

Summary statistics (n, mean, median, SD, minimum, and maximum) and the change and percent change from baseline to each scheduled study assessment will be presented by treatment group.

Box plots of absolute value over time and a line graph of mean change (and SD) from baseline to each scheduled study assessment may be presented for each treatment group.

A by-subject listing will also be presented.

4.3.2.5 All-cause mortality at Day 90

The number and percentage of subjects who have died (all-cause and ‘related to disease under investigation’ as recorded in the DEATH eCRF), those still alive, those with unknown survival status (lost to follow-up), those who have withdrawn consent and those censored for any other reason at Day 90 will be summarized by treatment group.

Kaplan-Meier (KM) plots and summary statistics will be presented for survival time by treatment group. The proportion of subjects alive at Day 90 will be defined as the KM estimate of overall survival at 90 days. This will be presented, along with its 90% CI. The computation of the CI will be based on a log-log transformation.

The method for handling subjects that withdraw or are lost to follow up on or prior to Day 90 is detailed in Section 3.1.6.

Subgroup analyses on COVID-related deaths may be performed as appropriate.

4.3.2.6 Alive and discharged from the ICU at Days 14 and 28

A summary of the number and percentage of subjects alive and discharged from the ICU at Day 14 will be presented. This will be repeated for Day 28. Analyses may be repeated for the PPAS, using the definition of the PPAS in Section 3.1.7.

The method for handling subjects that withdraw or are lost to follow up on or prior to Day 14 (or Day 28) is detailed in Section 3.1.7.

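### The per-protocol formula for alive and discharged from the ICU (SAP 3.1.7) counts subjects free of respiratory failure, contradicting the section's own definition; the error is confined to an optional secondary analysis

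*SAP*

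**What the plan says.** SAP 3.1.7 opens with the endpoint: "This is defined as the proportion of subjects alive and discharged from the ICU at Day 14", and likewise at Day 28. It then states what discharge means: "For a subject to be considered discharged from the ICU, they must not be in ICU on Day 14 (or Day 28"). It also limits the data that matter: "Only the subject's survival status and ICU status on Day 14 (or Day 28) will be considered for this endpoint".

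Two missing-data rules follow. In the FAS, subjects who withdraw or are lost on or before the day stay in the denominator as failures. In the PPAS they are excluded. Both sentences describe what cannot be assessed as survival and respiratory status, and the FAS sentence describes the imputed failure as death or respiratory failure. The PPAS percentage is then displayed as a fraction with numerator "Number of subjects alive and free of respiratory failure at Day 14 (or Day 28") and denominator "Number of subjects who have died or are still in the study at Day 14 (or Day 28").

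The analysis section, SAP 4.3.2.6, plans a number and percentage at each day and adds: "Analyses may be repeated for the PPAS, using the definition of the PPAS in Section 3.1.7". It gives no other formula. SAP Table 4 lists the FAS alone for this endpoint.

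**The concern.** The prose and the formula in one section describe different endpoints. Respiratory failure is defined in SAP 3.1.1 by the device in use: intubation with mechanical ventilation, high-flow nasal oxygen above stated limits, non-invasive positive pressure, or ECMO. ICU status is a location and level-of-care item taken from the CHCSS eCRF page. The two can differ for a given subject on a given day. A subject in ICU on low-flow oxygen succeeds under the formula and fails under the definition. A subject on qualifying high-flow oxygen outside the ICU does the reverse.

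A programmer who follows the displayed formula would produce a table with an ICU title and respiratory-failure content. At Day 28 it would match the PPAS result for the primary endpoint, which SAP 4.3.1.1 does plan. That agreement would be built in and would say nothing about ICU use.

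**Working it through.** The documents give no assumed rate, power or precision for the ICU endpoint, so there is no planned figure to reproduce. The check compares the formulas term by term and then shows the effect with assumed counts.

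**1. Formulas side by side**

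| | SAP 3.1.7, ICU endpoint, PPAS | SAP 3.1.1, respiratory failure at Day 28, PPAS |
|---|---|---|
| Numerator | "Number of subjects alive and free of respiratory failure at Day 14 (or Day 28") | "Number of subjects alive and free of respiratory failure at Day 28" |
| Denominator | "Number of subjects who have died or are still in the study at Day 14 (or Day 28") | "Number of subjects who have died or are still in the study at Day 28" |

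At Day 28 the two fractions are the same. At Day 14 the 3.1.7 fraction is the same as the one displayed in 3.1.2. (The prose in 3.1.2 mentions only loss to follow-up, whereas 3.1.7 also mentions withdrawal, but the displayed denominators agree.)

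**2. Size of the difference, in general**

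For one arm of the PPAS, let D be the denominator, d the deaths and r the subjects alive in respiratory failure. Let a be those alive, free of respiratory failure and in ICU, and b those alive, in respiratory failure and not in ICU.

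- As written: (D − d − r) / D
- By the section's definition: (D − d − (r − b) − a) / D
- Difference, definition minus formula: (b − a) / D

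The formula contains neither a nor b, so it cannot respond to ICU status. Disagreements in opposite directions cancel.

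**3. Illustration (assumed counts, not from the documents): D = 30, d = 3, r = 4**

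| a | b | As written | By the definition |
|---|---|---|---|
| 0 | 0 | 23/30 = 76.7% | 23/30 = 76.7% |
| 1 | 1 | 23/30 = 76.7% | 23/30 = 76.7% |
| 4 | 0 | 23/30 = 76.7% | 19/30 = 63.3% |
| 0 | 2 | 23/30 = 76.7% | 25/30 = 83.3% |

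Over a from 0 to 4 and b from 0 to 2, the correct figure runs from 63.3% to 83.3%. Each uncancelled subject moves it by 1/30 = 3.3 points.

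**4. FAS**

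Section 3.1.7 displays no fraction for the FAS, so the prose definition governs the numerator. Subjects who withdraw or are lost count in the denominator and not in the numerator, whether the imputed failure is called respiratory failure or being in ICU. The FAS percentage is the same under either wording.

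**The case against.** The best defence is that the intent is plain. The prose of 3.1.7 is correct, the formula looks carried over from 3.1.1 and 3.1.2, and a careful programmer would query it. Reach is also small. Table 4 uses the FAS, the PPAS repeat is optional, and the endpoint is a descriptive secondary one that is absent from the DMC outputs in SAP 8.2. The Day 14 duplication needs two optional repeats, because SAP 4.3.2.1 also leaves its PPAS analysis open. All of this stands and limits the point. It does not make the formula right: 4.3.2.6 refers to 3.1.7 for the PPAS, and the only fraction written there is the wrong one.

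A reader might go further in four ways that the documents do not support.

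- *That the trial never measures ICU status.* The FAS analysis follows the prose definition and does measure it.
- *That the FAS rule misses subjects with known respiratory status but unknown ICU status.* The rule is triggered by withdrawal or loss to follow-up. Protocol 8.4.3 has ICU care recorded for each day in hospital up to Day 90, so such a subject is hypothetical.
- *That most subjects never enter ICU, so that discharged is a misnomer.* Exclusion criterion 1 bars respiratory failure only where it impedes swallowing pills, together with subjects likely to need mechanical ventilation within 24 hours and so be unable to swallow them. Subjects in respiratory failure who can swallow may enrol. No document gives an ICU admission rate. Counting never-admitted subjects as successes follows from a rule the SAP states openly, under the protocol's own endpoint name.
- *That the error per discordant subject can be fixed from the 62 randomized.* Half of 62 is an FAS-sized arm. The formula applies to the PPAS, a subset that also drops withdrawn and lost subjects, and its size is not given.

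**Conclusion.** Wrong as written, and limited to an optional secondary analysis. The PPAS formula in SAP 3.1.7 contradicts the definition in the same section. Run as written, it returns the PPAS respiratory-failure percentages of 3.1.1 and 3.1.2 exactly. That follows from the displayed fractions and needs no assumption.

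How far the result would lie from the true ICU figure is (b − a)/D. The documents supply none of these counts, so the 63.3% to 83.3% range is an illustration and not an estimate. The FAS result and the primary endpoint are untouched. The respiratory wording in the FAS sentence is a drafting fault without numerical effect.

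**What to change.** In SAP 3.1.7:

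- Replace the PPAS numerator with *Number of subjects alive and not in ICU at Day 14 (or Day 28)*. Leave the denominator as it is.
- In the FAS and PPAS missing-data sentences, change *respiratory status* to *ICU status*. In the FAS sentence, change *had a respiratory failure* to *were in ICU*. This aligns the wording and leaves the FAS result unchanged.

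The cost is a short SAP correction and, if the PPAS repeat is programmed, one derivation line. Survival and ICU status are already collected. Neither a new title nor an added ICU subgroup is needed to cure the defect.

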3.1.8 Time to first occurrence of respiratory failure or death

This is defined as the time (in days) from randomization to the first occurrence of respiratory failure or death (due to any cause) on study (up to Day 28), whichever occurs first.

If a subject does not have an event (i.e., does not experience respiratory failure or death) on or before Day 28 and does not withdraw or become lost to follow up from the study on or prior to Day 28, the data will be censored at Day 28. If a subject does not have an event but withdraws from the study or is lost to follow up on or prior to Day 28, the data will be censored at the last date known that the subject was alive and free of respiratory failure up to Day 28.

Subjects with respiratory failure at baseline (defined as respiratory failure on the date of randomization (Day 1)) will not be included in any analyses of time to first occurrence of respiratory failure or death.

Subjects with respiratory failure at baseline (described in Section 3.5.1) will not be included in any analyses of time to first occurrence of respiratory failure or death.

3.1.9 Days alive and free of respiratory failure over the course of 28 days

This is defined as the total number of days alive and free of respiratory failure from randomization to Day 28.

For a day to count as ‘alive and free of respiratory failure’, the subject must be free of respiratory failure for the entire day. All days from the start date to the stop date inclusive of each respiratory failure will count as respiratory failure days. If a subject dies on Day 1, the number of days alive and free of respiratory failure is zero. If a subject is alive on Day 28 and has not experienced respiratory failure at any point over the 28 day period, the number of days alive and free of respiratory failure is 28 days.

The following rules will be applied for missing data:

- If a subject has been discharged from hospital and is known to be alive at Day 28, and there is no evidence that respiratory failure has occurred during this period, the number of days from being discharged to Day 28 will be counted as days alive and free of respiratory failure. If a subject has been discharged from hospital but dies on or prior to Day 28 and there is no evidence that respiratory failure has occurred during this period, the number of days from being discharged to the last date known to be alive will be counted as days alive and free of respiratory failure.
- If a subject has been discharged from hospital but dies on or prior to Day 28 and there is evidence of respiratory failure during this period, the number of days from being discharged to the last date known to be free of respiratory failure will be counted as days alive and free of respiratory failure.
- If a subject withdraws from the study or is lost to follow up on or prior to Day 28, the days with unknown survival/respiratory failure status will be considered as follow:
 - If the subject is discharged from hospital at the time they withdraw from the study or are lost to follow up, days from last known status to Day 28 (or date

last known to be alive if death is known, whichever occurs first) will be counted as days alive and free of respiratory failure.

- If a subject is in hospital and is not experiencing respiratory failure at the time they withdraw from the study, days from last known status to Day 28 (or date last known to be alive if death is known, whichever occurs first) will be counted as days alive and free of respiratory failure.
- If the subject is in hospital and is experiencing respiratory failure at the time they withdraw from the study, days from last known status to Day 28 will be assumed as experiencing respiratory failure.

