6.1 Treatments Administered

6.1.1 Dosing and Duration of Treatment

Acalabrutinib treatment should be administered within 6 hours of randomization on Day 1.

Subjects will take acalabrutinib 100 mg capsules by mouth bid for 10 days (a maximum of 20 doses). Capsules will be taken with water. The capsules should be swallowed intact and subjects should not attempt to open capsules or dissolve them in water. For subjects requiring a proton-pump inhibitor (PPI), acalabrutinib must be administered as described in Section 6.1.3.1.

Acalabrutinib can be taken with or without food.

Retreatment with acalabrutinib is not allowed.

BSC will be administered in both arms per Investigator's discretion and institutional guidelines.

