8.4 Clinical Assessments During Hospitalization

8.4.1 Oxygen Treatments and Ventilator Use

If a subject requires oxygen supplementation, data will be recorded, including method of oxygen supplementation, maximum daily flow rate and fraction of inspired oxygen (FiO₂).

If a subject requires mechanical ventilation, data will be recorded regarding whether ventilator weaning was attempted.

For subjects on mechanical ventilation the following ventilator settings will be recorded: tidal volume, FiO2, peak airway pressure over the last 24 hours, plateau pressure, positive end expiratory pressure, and respiratory rate. The data will be recorded qd, and the worst value of the day will be entered

For subjects on mechanical ventilation, an arterial blood gas (pH, partial pressure of oxygen [PaO₂], partial pressure of carbon dioxide [PaCO₂], and FiO₂ at the time the sample was obtained), will be recorded qd. If more than one value is obtained for the arterial blood gases, the value closest to 08:00 will be used.

Arterial gasses should be collected from subjects if the sample is easily accessible and the procedure will not be painful to subjects (ie, subject is in the ICU or has arterial port). All available data from the arterial gases should be entered into the database. If the collection of arterial gases is not clinically indicated, the test should not be performed.

Predicted body weight will be recorded on the ventilator eCRF for assessment of tidal volume.

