3.4 Exploratory pharmacodynamic and correlative variables

3.5 Other variables

3.5.1 Baseline characteristics

Baseline characteristics that will be collected or derived are:

- Demographics: Age (years), sex, race and ethnicity
- Subject characteristics: Weight, height and body mass index (BMI), where $BMI (kg/m^2) = Weight/Height^2$
- Medical history: Name of past and/or concomitant diseases (verbatim and coded using the MedDRA dictionary version 23.0), start and stop dates
- Relevant surgical history: Surgical procedure (verbatim and coded using the MedDRA dictionary version 23.0)
- Pregnancy status for applicable subjects only: test date and result (positive or negative)

- History of substance abuse: cigarettes (former/current/never), vaping (former/current/never), recreational inhaled drugs (former/current/never), alcohol (former/current/never)
- SARS-CoV-2 infection comorbidities: infection comorbidities prior to admission, subcategory, comorbidity start and stop date
- SARS-CoV-2 infection risk factors/lifestyle events: infection risk factor, infection risk factor start and stop date
- SARS-CoV-2 infection signs and symptoms: infection signs or symptoms, clinical event start and stop date
- Respiratory failure status at baseline (with vs without), as defined in [Table 1](#), where baseline is defined as the result obtained on the date of randomization (Day 1)
- Intensity of oxygen treatment and mechanical ventilation at baseline: most extreme oxygen treatment or mechanical ventilation, flow rate
- Intensity of oxygen treatment and mechanical ventilation prior to baseline: most extreme oxygen treatment or mechanical ventilation, flow rate, duration of treatment

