- Baseline is defined as the result obtained on the day of randomization (Day 1) only. Applies to:
 - Respiratory failure status at baseline
 - Baseline oxygen saturation (SpO₂)
 - Baseline for all oxygen and mechanical ventilation assessments
 - Baseline ordinal scale score
 - Baseline mSOFA score
- For all summaries, change from baseline variables will be calculated as the post-baseline value minus the value at baseline. The percentage change from baseline will be calculated as $((\text{post-baseline value} - \text{baseline value}) / \text{baseline value}) \times 100$.
- Unless stated otherwise, visit windows will apply as follows:
 - Day 1 (date of randomization): No window unless specified above (where latest result prior to date of randomization can be used)
 - Days 2-10 or discharge (whichever occurs first): no visit window. Note: if a subject is discharged prior to Day 7 they will visit the site for an assessment 2 to 4 days after discharge. Assessments should match those for Day 10.

- Day 14: ± 2 days
- Day 28: ± 3 days
- Arm 1 Safety follow-up at 28 days after last dose of acalabrutinib: ± 3 days
- Arm 2 Safety follow-up (for AEs, concomitant medications and survival assessment) at 38 days after randomization: ± 3 days
- Long-term follow-up 90 days after randomization: ± 7 days
- Observations recorded on the date closest to the scheduled assessment day (as long as this is within the visit window) will be used as the scheduled assessment. If Any observations recorded outside of the visit window will be considered unscheduled visit observations and will not be included in visit-based summaries at a treatment-group level. If multiple observations are recorded per day, or observations within a visit window are equidistant from the target day, the worst assessment reported will be used as the scheduled assessment. For laboratory and vital signs assessments, this is the maximum reported value.
- Visit-based summaries will include: Baseline (Day 1), Day 2-10, Day 14 and Day 28 where applicable, as per SoA.
- For listings at a subject level, all values will be included (regardless of whether they appear in a corresponding visit-based summary) when deriving a patient level statistic such as a maximum.

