4.2.3 Demographic and other baseline characteristics

Demographic and other baseline characteristics will be listed for all subjects and summarized by treatment group and overall for the FAS using the rules for summarizing continuous and categorical variables described in Section 4.1.

In addition to being summarized as continuous variables, age, and BMI will be summarized as the following categorical variable: age group (<65 , ≥ 65 years, as well as categories of <20 , ≥ 20 - < 35 , ≥ 35 - < 50 , ≥ 50 - <65 , ≥ 65 - <75 , ≥ 75 years.) and BMI group (Underweight [<18.5], Normal [18.5 - <25.0], Overweight [25.0 - <30.0] and Obese [≥ 30.0]).

The number and percentage of subjects with comorbidities for each treatment group will also be presented, as well as the number of comorbidities (e.g. the number and percentage of subjects in each treatment group with 1, 2, 3, etc. comorbidities) and type.

The number and percentage of subjects with signs and symptoms at screening for each treatment group will be presented overall and by onset time relative to randomization.

The most extreme oxygen treatment or mechanical ventilation received at baseline will also be summarized (most extreme to least extreme: ECMO, invasive ventilation, non-invasive ventilation). If the subject's most extreme treatment is oxygen (no mechanical ventilation was received), maximum oxygen flow rate will be summarized. This will be repeated for prior to baseline, and in addition the duration of any oxygen treatment or mechanical ventilation will be summarized continuously and categorically.

Medical history and surgical history are coded using MedDRA (version 23.0) and will be summarized by System Organ Class (SOC) and Preferred Term (PT).

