4.3.2.9 Days with respiratory failure over the course of 28 days

Summary statistics (n, mean, median, SD, minimum, and maximum) of the number of days with respiratory failure over 28 days will be presented by treatment group. In addition, the number and percentage of subjects in the following categories will be presented, 0 days, 1-6 days, 7-14 days, 15-21 days, and 22-28 days.

A bar chart of the number of days with respiratory failure for each subject within the treatment group will be produced, i.e., showing graphically the distribution of the number of days with respiratory failure for each treatment group.

The proportion of subjects who experienced respiratory failure or died over the course of 28 days will also be summarized by treatment group. Subjects with respiratory failure on the day of randomization will be excluded from this summary.

Furthermore, the proportion of subjects who required invasive ventilation or ECMO or died over the course of 28 days will be summarized by treatment group.

The method for handling deaths and subjects that withdraw or are lost to follow up on or prior to Day 28 is detailed in Section [3.1.10](#).

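### A respiratory failure that begins after randomization on Day 1 is coded as baseline, which removes the subject from the time-to-first-failure-or-death analysis and the 28-day failed-or-died proportion

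*SAP*

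**What the plan says.** SAP 3.1.8 measures time to first respiratory failure or death from randomization and then states: "Subjects with respiratory failure at baseline (defined as respiratory failure on the date of randomization (Day 1)) will not be included in any analyses". SAP 4.3.2.9 says of the 28-day failed-or-died proportion: "Subjects with respiratory failure on the day of randomization will be excluded from this summary". SAP 4.1 fixes the general rule for respiratory failure status and for all oxygen and ventilation variables: "Baseline is defined as the result obtained on the day of randomization (Day 1) only". SAP 3.5.1 uses the same date for the baseline characteristic. None of these sections requires onset to precede randomization.

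Day 1 extends past randomization. For Arm 1, Protocol 6.1.1 says: "Acalabrutinib treatment should be administered within 6 hours of randomization on Day 1". Protocol 8.4.1 says of ventilator settings: "The data will be recorded qd, and the worst value of the day will be entered". For supplemental oxygen it records the method and the maximum daily flow. SAP 4.1 adds that the worst of several same-day observations is used.

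The Day 1 classification also enters the supplementary logistic model for the primary endpoint and the baseline-failure subgroup (SAP 4.3.1.1), and that subgroup again at Day 14 (SAP 4.3.2.1). The failed-or-died proportion is on the list of DMC outputs (SAP 8.2). SAP 3.5.1 also lists "Intensity of oxygen treatment and mechanical ventilation prior to baseline", and SAP 4.2.3 plans to summarize it: "This will be repeated for prior to baseline".

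**The concern.** Leaving out subjects who are already in respiratory failure at randomization is sound. Exclusion criterion 1 admits such subjects if they can still swallow pills, and they are not at risk of a first failure. Protocol 9.6.2 leaves such detail to the SAP. The difficulty is only where the line is drawn.

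A subject who is free of failure at randomization and goes onto high-flow oxygen or non-invasive ventilation that evening has had the event the endpoint is meant to capture. Under the date rule that subject is removed from the analysis. For these onsets the rule is a post-randomization exclusion based on the outcome. The trial is open-label, and respiratory failure is defined by resource use that clinicians choose knowing the arm. In the logistic model and the subgroups, the same event becomes a baseline trait.

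At stake are one secondary endpoint, one summary that the DMC sees, one supplementary estimate, and one subgroup at two time points.

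**Working it through.** **Step 1. The plan's own figure.** Protocol 9.2 assumes 70% versus 90% alive and free of respiratory failure at Day 28, 30 per arm, two-sided alpha 0.10, unpooled variance.

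- SE = sqrt(0.70×0.30/30 + 0.90×0.10/30) = sqrt(0.007 + 0.003) = 0.100.
- Half-width = 1.645 × 0.100 = 16.4 points, as stated.
- Power = Φ(0.20/0.100 − 1.645) = Φ(0.355) = 63.9%, against the stated 64%.

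These figures concern the primary endpoint, and the Day 1 rule does not change them. They give a scale for what follows.

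**Step 2. Assumptions.** The documents give no number of Day 1 onsets and no rate of ever failing or dying. I assume 30 at risk per arm and 9 (BSC) versus 3 (acalabrutinib) first events. This borrows the complements of the Day 28 rates. It is illustrative only, because Day 28 status counts recovered failures as successes. I then let one event in an arm be a Day 1 onset and exclude that subject.

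**Step 3. One excluded onset.** For constant hazards, HR = ln(1 − p_acalabrutinib) / ln(1 − p_BSC).

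| Onset excluded | Failed-or-died difference | HR |
|---|---|---|
| none | 9/30 − 3/30 = 20.0 points | ln(27/30)/ln(21/30) = 0.295 |
| one BSC | 8/29 − 3/30 = 17.6 | ln(27/30)/ln(21/29) = 0.326 |
| one acalabrutinib | 9/30 − 2/29 = 23.1 | ln(27/29)/ln(21/30) = 0.200 |
| one in each arm | 8/29 − 2/29 = 20.7 | ln(27/29)/ln(21/29) = 0.221 |

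A simulated stratified Cox fit shows the width of the interval. It used four near-equal strata, Efron ties, a 90% profile-likelihood CI, the Day 1 onset at t = 1, other events uniform on Days 2 to 14, censoring at Day 28, and medians of 120 draws. With one BSC onset, 0.30 (0.09 to 0.83) becomes 0.33 (0.10 to 0.95). With one acalabrutinib onset, 0.31 (0.09 to 0.86) becomes 0.20 (0.04 to 0.64).

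**Step 4. Other event counts, closed form.** The order is one BSC, one acalabrutinib, one in each arm. With 9 versus 6 events, 0.626 becomes 0.691, 0.531 or 0.586. With 9 versus 9, 1.000 becomes 1.105, 0.905 or 1.000.

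**Step 5. More than one onset in the same arm.** At 9/30 versus 3/30:

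- Excluding three BSC onsets gives 6/27 − 3/30 = 12.2 points.
- Excluding three acalabrutinib onsets gives 9/30 − 0/27 = 30.0 points.

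With no true difference (6/30 in each arm), excluding one, two or three onsets from one arm creates a gap of 2.8, 5.7 or 8.9 points (6/30 − 5/29, 6/30 − 4/28, 6/30 − 3/27).

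**Step 6. Supplementary outputs.** Assume 21/30 versus 27/30 Day 28 successes and three true baseline failures per arm, with successes of 1/3 and 20/27 (BSC) and 2/3 and 25/27 (acalabrutinib) with and without baseline failure. A logistic model with treatment and baseline failure, strata omitted, gives a standardized difference of 20.0 points. Recoding one Day 28 non-success as baseline failure gives 18.7 (BSC), 21.5 (acalabrutinib) or 20.0 (one each). In the subgroup without baseline failure, 25/27 − 20/27 = 18.5 points becomes 25/27 − 20/26 = 15.7, 25/26 − 20/27 = 22.1, or 25/26 − 20/26 = 19.2.

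**The case against.** The strongest reply is that little is hidden. SAP 4.3.2.9 tabulates days with respiratory failure in the full analysis set with a separate zero-days category and no Day 1 exclusion. SAP 3.1.10 counts every failure from its start date and treats the days from death to Day 28 as failure days. The complement of zero days is therefore close to an all-randomized failed-or-died count. Baseline failure status is tabulated by arm and goes to the DMC, so the total excluded is visible. By-subject oxygen and ventilation listings are planned (SAP 4.4.6). Deaths stay in Day 90 mortality. All of this stands. A reader might infer that no planned output shows any effect of the rule, or that these subjects vanish from the efficacy results. The documents support neither inference. What remains unshown is the split between failure before randomization and Day 1 onset, and a hazard ratio without the exclusion.

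A second reply is that a date-level rule may be all the data allow: the SAP amendment history attributes the baseline definition to limited data collection. That is a good reason to keep the rule for the main analysis. It does not rule out a sensitivity run, because SAP 3.1.9 and 3.1.10 already rely on start and stop dates of each failure. Whether onset times exist is not shown. The worst-value recording in Protocol 8.4.1 concerns ventilator settings and does not settle how onset is captured.

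Third, numbers should be small: criterion 1 bars subjects expected to need mechanical ventilation within 24 hours and so be unable to swallow pills. That also stands, although the clause does not mention expected high-flow oxygen.

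**Conclusion.** The point holds as a boundary problem of limited scope. The affected outputs are the time-to-first-failure-or-death analysis, the failed-or-died proportion, the supplementary logistic estimate, and the baseline-failure subgroup at Days 14 and 28. Not affected are the Day 28 arm proportions, their difference with its CI, the Cochran-Mantel-Haenszel and chi-square tests, the two respiratory-failure days endpoints, the proportion needing invasive ventilation or ECMO or dying, and Day 90 mortality.

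On assumed counts, one excluded onset shifts the failed-or-died difference by about 2 to 3 points, which is small against 16.4. Three in one arm would shift it by about 8 to 10 points, but nothing in the documents says this happened. A reader might also infer that the rule favours acalabrutinib. The direction depends on which arm has the onsets, and the documents do not say. This is a cheap improvement to the SAP. It does not threaten the trial's main result.

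**What to change.** Keep the date rule as the main analysis and add two items to SAP 4.3.2.7 and 4.3.2.9.

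- (a) A count by arm of Day 1 failures with and without a respiratory-failure record that starts before the date of randomization. Use the start dates the SAP already relies on and the prior-to-baseline support data. This alone may show that the issue is trivial.
- (b) One sensitivity run of the time-to-event endpoint and of the failed-or-died proportion. Exclude only subjects whose failure has a recorded start before the date of randomization and is ongoing on Day 1, and count all other Day 1 failures as Day 1 events. The most extreme prior support should not be used for this, because it can include subjects who had already been weaned.

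If onset times turn out to be recorded, compare them with the randomization time in the IRT instead. A logistic fit using pre-Day 1 failure status is optional.

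The cost is SAP text, one small table, one extra time-to-event run and one extra proportion. No new collection is needed if the recorded start dates reach back before Day 1, which should be confirmed.

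The downside is that failures that began on Day 1 before randomization, or that have no earlier record, count as events in (b). The two analyses therefore show sensitivity and need not bracket the truth. Suppose the BSC Day 1 failure began after randomization and the acalabrutinib one before it. The date rule gives 8/29 − 2/29 = 20.7 points and (b) gives 9/30 − 3/30 = 20.0, while the true difference is 9/30 − 2/29 = 23.1.
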